9.2 Case Report Form completion

The eCRF will be presented in an electronic casebook comprising a series of electronic forms. The Subject Number should always be indicated and date (and time, if applicable) of each assessment should be entered in the eCRF.

The eCRFs must be completed in timely manner so that this does not delay the ongoing data validation, review and quality control. The final, completed eCRF for each subject must be electronically signed and dated by the Investigator on the appropriate eCRF form to signify that he/she has reviewed the electronic casebook and certifies it to be complete and accurate.

The eCRF will feature a special means for correcting errors in the previously entered data. A complete audit trail of the original entries, changes and deletions, session dates and times and the credentials of the eCRF user who performed the operation will be maintained by the system.

9.3 Data processing

The data collected on the eCRFs will be captured in a specially constructed and validated database. The data will be validated using both manual and electronic means. Clarification of data will be requested from the Investigator site as required. An audit trail of the original database entries, changes and deletions, session dates and times and the credentials of the database user who performed the operation will be maintained by the system. The completed database will be quality assured and locked to prevent further changes. A full database extract will be made available for statistical analysis according to the methods outlined in Section 10 and the Statistical Analysis Plan (SAP).

AEs and medical history entries will be coded using the Medical Dictionary for Regulatory Activities (MedDRA). Concomitant medications will be coded using the World Health Organization (WHO) Drug Dictionary. Versions of the dictionaries used will be documented in the data management plan and SAP.

10 STATISTICAL METHODS AND PLANNED ANALYSES

10.1 Determination of sample size and randomization

There is no formal estimation of sample size for inclusion of subjects in Study MT-8554-A02. It is planned to enroll up to 364 subjects who have completed Study MT-8554-A01 and who comply with all eligibility criteria for Study MT-8554-A02.

Study MT-8554-A02 is an open-label extension study of Study MT-8554-A01. All subjects will receive MT-8554 (was 10 mg initially, switched to 5 mg) for 52 weeks. Subjects will not be randomized.

10.2 Analysis sets

Statistical analyses will be based on separate population sets, defined in Table 4.

Table 4 Analysis populations

Analysis Population	Definition
Safety population	All subjects who receives at least 1 dose of study medication
Intent-to-treat (ITT) population	All subjects who have at least 1 post-baseline efficacy assessment

The Safety population will be used for all analyses and summaries. The ITT population will be used for all clinical efficacy analyses.

10.3 Statistical analysis

10.3.1 General considerations

A SAP containing definitions of analysis populations and baseline points, detailed data handling, analysis methods, detailed methods and criteria for the interim analysis, and outputs (tables, figures and listings) will be developed and approved prior to database lock. Additional analysis may be performed if deemed necessary. Any deviations from the planned analysis will be described and justified in a separate document and in the CSR.

The statistical analysis will be performed using SAS® Version 9.2 or higher. The Safety population will be used for all analyses and summaries. Point estimates will have 2-sided 95% CIs where applicable.

Where appropriate, data will be summarized descriptively (frequency and percent will be summarized for categorical variables; mean, standard deviation, median, minimum, and maximum will be presented for continuous variables) by study visit and by treatment group.

All individual subject data will be listed, where applicable. The baseline value of Study MT-8554-A02 is the last valid values prior the first dose of Study MT-8554-A02. The baseline value of Study MT-8554-A01 and Study MT-8554-A02 will be used as appropriate.

The Study MT-8554-A01 data are combined with Study MT-8554-A02 data for summary tables and graphs as needed.

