**LIST OF ABBREVIATIONS**

Abbreviation	Definition
AE	Adverse event
ALP	Alkaline phosphatase
ALT	Alanine aminotransferase
AST	Aspartate aminotransferase
BDRM	Blind data review meeting
BLQ	Below the limit of quantification
BMI	Body mass index
BUN	Blood urea nitrogen
CI	Confidence interval
CPK	Creatine phosphokinase
CRF	Case Report Form
CRO	Contract Research Organization
CS	Clinically significant
CSR	Clinical study report
DMC	Data Monitoring Committee
DP	Decimal places
E2	Estradiol
ECG	Electrocardiogram
eCRF	Electronic Data Collection Form
EOS	End of study
EOT	End of treatment
FDA	Food and Drug Administration
Fmi	Daily frequency of mild VMS
Fmo	Daily frequency of moderate VMS
Fse	Daily frequency of severe VMS
FSH	Follicle stimulating hormone
GAD7	7-Item Generalized Anxiety Disorder questionnaire
GCP	Good Clinical Practice
IAO	International Agreed Order
ICF	Informed Consent Form
ICH	International Conference on Harmonization

Abbreviation	Definition
IEC	Independent Ethics Committee
IRB	Institutional Review Board
IMP	Investigational medicinal product
IND	Investigational New Drug Application
ITT	Intent-to-Treat
IVRS	Interactive Voice Response System
IWRS	Interactive Web-based Response System
LDH	Lactate dehydrogenase
LDL-C	Low density lipoprotein-cholesterol
LH	Luteinizing hormone
LLOQ	Lower limit of quantification
MCH	Mean corpuscular hemoglobin
MCHC	Mean corpuscular hemoglobin concentration
MCV	Mean corpuscular volume
MedDRA	Medical Dictionary for Regulatory Activities
MENQOL	Menopause-Specific Quality of Life questionnaire
MsFLASH	Menopausal Strategies: Finding Lasting Answers to Symptoms and Health
MTDA	Mitsubishi Tanabe Pharma Development America, Inc.
MTPC	Mitsubishi Tanabe Pharma Corporation, Inc.
NCS	Not clinically significant
PHQ-8	8-Item Patient Health Questionnaire
PT	Preferred term
QC	Quality control
QOL	Quality of life
QTc	Corrected QT interval
QTcF	Corrected QT interval using Fridericia's formula
RBC	Red blood cells
SAE	Serious adverse event
SAF	safety population
SAP	Statistical Analysis Plan
SD	Standard deviation

Abbreviation	Definition
SNRI	Serotonin-norepinephrine reuptake inhibitors
SOC	System Organ Class
SSRI	Serotonin reuptake inhibitors
SUSAR	Suspected unexpected serious adverse event
TEAE	Treatment-emergent adverse event
THC	Tetrahydrocannabinol
ULN	Upper limit of normal
US	United States
VMS	Vasomotor symptoms
WBC	White blood cells
WHO	World Health Organization
WMA	World Medical Association

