## **6. GENERAL CONSIDERATIONS**

### **6.1 Descriptive Statistics**

Continuous data will be summarized descriptively using the number of observations, mean, standard deviation (SD), median, minimum and maximum. Categorical data will be summarized using frequency counts and percentages. The denominator for the percentages will be the total number of subjects in the treatment group and analysis population being presented, unless otherwise specified.

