### 8.2.7.2 Endometrial Histology (Endometrial Biopsy)

The Endometrial biopsy data will be summarized in the tables by treatment group of A01 and overall and visit as below.

1. Summary tables of proportion of subjects in abnormal\* category (Table 14.3.7.1)
2. Shift table for change in abnormal category from baseline to week 64 or EOT(Table 14.3.7.2)

\*Note: The histological categories are based on 2003 draft FDA guidance. [REDACTED]

[REDACTED]

[REDACTED]

[REDACTED]

The data from adjudication committee will be used for the analysis.

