## 9. DATA PRESENTATION CONVENTIONS

### 9.1 Number of Digits to Report

**Table 7 Number of decimal places (DP) or significant digits (SD)**

Statistic	Specification	Apply to
Minimum, maximum	same number of DPs as the data provided in the datasets	All original, i.e. non-derived, data provided in the datasets
	See section 7.3	All derived data
Mean, Median	one more DP than above	All
SD, SE	two more DP than above	All
Percentages*	1 DP	All

\*Percentages: use 1 place beyond the decimal point, except for the following cases:

If the percentage is equal to 0, then leave blank, do not use (0)

If the percentage is equal to 100, then use "(100)" without a decimal

Listings will be presented in subject, visit (where applicable) and date (where applicable) order. Listings will be produced (landscape in MS Word) using PROC REPORT in SAS monospace font and pitch 8.

Summary tabulations will be presented by treatment group of study A01 and overall if appropriate, scheduled visit order (if appropriate). Continuous data summaries will present (unless stated otherwise) number of observations, mean, standard deviation, median, minimum and maximum. Categorical data summaries will present the number of observations and the corresponding percentage.

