## **10. CHANGE FROM THE PROTOCOL**

Protocol says “Baseline VMS severity score is defined as  $(2xFmo + 3xFse)/(Fmo + Fse)$ , and VMS severity score for a specific week during the open label treatment period is defined as  $(1xFmi + 2xFmo + 3xFse)/(Fmi + Fmo + Fse)$ , where Fmi, Fmo, and Fse are the daily frequencies of mild, moderate, and severe VMS, respectively, during each applicable study week.”. However, the baseline VMS severity score is from the end of treatment of study A01. The VMS severity score there is defined as  $(1xFmi + 2xFmo + 3xFse)/(Fmi + Fmo + Fse)$ . So this formula is used for baseline VMS severity score in A02.

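### The protocol provides for 2-sided 95% confidence intervals where applicable, but no readable SAP rule plans any, and the default denominator would dilute the biopsy proportions

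*Protocol*

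**What the plan says.** **Protocol.** Section 10.3.1 states: "Point estimates will have 2-sided 95% CIs where applicable". A separate paragraph of that section lists the descriptive statistics. The section also says that departures from the planned analysis will be explained in a separate document and in the study report. Sections 10.3.4 and 10.3.5 leave further detail to the SAP.

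**SAP, general rules.** Section 6.1 states: "Continuous data will be summarized descriptively using the number of observations, mean, standard deviation (SD), median, minimum and maximum", and "Categorical data will be summarized using frequency counts and percentages". Its default denominator for percentages is every subject in the treatment group and population being shown, unless specified otherwise. Section 9.1 repeats the pattern: "Categorical data summaries will present the number of observations and the corresponding percentage". Its rule for zero percentages reads "If the percentage is equal to 0, then leave blank, do not use (0".

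**SAP, endpoint sections.** For endometrial histology, Section 8.2.7.2 plans "Summary tables of proportion of subjects in" the abnormal category, plus a shift table. The readable text on adverse events (8.2.1), laboratory criteria (8.2.2), ECG criteria (8.2.4), endometrial thickness (8.2.7.1) and exploratory endpoints (8.3) names no interval. The abbreviation list has an entry for "Confidence interval", but no readable method uses it.

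**SAP, declared changes.** Section 10 covers only the VMS severity formula at baseline, ending: "So this formula is used for baseline VMS severity score in A02".

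**The concern.** Long-term safety is the primary objective. The safety endpoints include the incidence of endometrial hyperplasia and of breast cancer, for which few or no events are plausible. There is no formal sample size calculation, so nothing else in the plan says how large a risk the study could exclude. An interval would say it.

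Two SAP conventions add to the gap. A row with no events would show a count and a blank where the percentage belongs, with no upper limit. And only women with a uterus have a biopsy (Protocol Table 1, footnote 8, and Section 6.5.6). If the default denominator of SAP 6.1 is applied to Table 14.3.7.1, women who could not have shown hyperplasia are counted as if they had been assessed, and the proportion comes out too low.

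**Working it through.** The documents give no sample size, power or precision figure, so there is nothing to reproduce first.

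**Step 1: compare the documents.** The protocol has a rule on intervals. The SAP's two general rules (6.1 and 9.1) list number, mean, SD, median, minimum and maximum, or count and percentage. The decimal-place table in 9.1 has a row for SD and SE but none for confidence limits. Section 10 is silent on intervals. The general rules are not redacted; parts of 8.2.1 and 8.2.7.2 are.

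**Step 2: inputs for size.**
- Enrolment cap: 364 (Protocol 4.1). The Safety population is everyone who takes at least one dose (Protocol 10.2), so it can be as large as 364.
- The study ends once about 100 women have finished 52 weeks of treatment and follow-up (Protocol 4.1, 4.6). This is a stopping rule and not an analysis denominator.
- Biopsies are taken at Week 12 and at Week 64 or early termination (Protocol 6.5.6), so completers do not cap the number of biopsies.
- The number of women with a uterus is not given. Assumption: 50 to 300 evaluable biopsies.

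**Step 3: zero events.** The exact 2-sided 95% upper limit solves (1 − p)^n = 0.025, so p = 1 − 0.025^(1/n).

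| n | Basis | Upper limit with 0 events |
|---|---|---|
| 50 | assumed low end | 1 − 0.025^(1/50) = 7.11% |
| 91 | assumed: 364/4, equal split over the four A01 groups | 1 − 0.025^(1/91) = 3.97% |
| 100 | illustrative; equals the completer target | 1 − 0.025^(1/100) = 3.62% |
| 300 | assumed high end | 1 − 0.025^(1/300) = 1.22% |
| 364 | enrolment cap | 1 − 0.025^(1/364) = 1.01% |

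Check: the probability of no events at the limit is 0.025 for n=100 and for n=364. The row for 91 matters because the SAP tables are split by A01 treatment group as well as shown overall.

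**Step 4: one event.** With Clopper-Pearson limits from beta quantiles, 1/100 = 1.0% has the interval 0.03% to 5.45%, and 1/364 = 0.27% has 0.01% to 1.52%.

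**Step 5: denominator.** Suppose, for illustration, 2 cases among 200 women with an evaluable biopsy in a Safety population of 364. Using women assessed, 2/200 = 1.0% (0.12% to 3.57%). Using the SAP 6.1 default, 2/364 = 0.55% (0.07% to 1.97%). The reported proportion shrinks by the factor 200/364 = 0.55. The size of the dilution depends on the assumed 200, but its direction does not.

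**The case against.** The best defence is that the protocol sentence is generic and qualified. It ends with a where-applicable clause, no individual endpoint in the protocol is assigned an interval, and the protocol's own list of descriptive statistics contains none. A reader might infer that the SAP dropped a specific promised analysis. The documents do not support that. What stands is narrower: incidence proportions are point estimates to which an interval plainly applies, and the SAP neither plans one nor says that none apply.

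A reader might also infer that the safety results would be bare percentages. They would not, because counts appear beside percentages and anyone could compute an exact limit. That recovers the right limit only if the denominator is right, which for biopsies it would not be by default.

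Three further points have some force. Table 7 of the SAP provides for an SE and Section 9.1 allows exceptions, but neither gives an exact limit for a rare proportion. The redacted text in 8.2.1 and 8.2.7.2 might name an interval or a biopsy denominator, so total absence cannot be asserted. And SAP Section 10 is not the only place to record a departure, since the protocol also names a separate document and the study report. Even so, Section 10 exists for this purpose and omits it.

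Finally, the study is descriptive and has no hypothesis test. This is correct, and it limits the consequence to reporting.

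**Conclusion.** The mismatch is real in the readable text, and it bears on the primary safety results. No error rate or decision rule is affected; what suffers is how precisely a rare or zero incidence can be interpreted.

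Its size should be given as a range. A reader might take the completer target of about 100 as the denominator and conclude that zero events can never exclude a rate below 3.6%. The documents do not support this, because the Safety population may reach 364 and biopsies are also taken at early termination. Over the assumed 50 to 300 evaluable biopsies, the zero-event limit runs from 7.1% to 1.2%. At the enrolment cap, which is the best case for outcomes assessed in everyone, it is 1.0%.

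The denominator problem is separate from the intervals. It rests on the SAP 6.1 default applying to the biopsy tables, which the readable part of 8.2.7.2 does not override.

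**What to change.** Before database lock, amend the SAP as follows.

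- **6.1:** plan exact (Clopper-Pearson) 2-sided 95% intervals for the incidence of endometrial hyperplasia, breast cancer, serious TEAEs and TEAEs leading to discontinuation of study medication.
- **8.2.7.2:** use women with an evaluable biopsy at the visit concerned as the denominator for biopsy results, and show that number in the table.
- **9.1:** for these outcomes, show a zero count with its upper limit instead of a blank, and add a decimal-place rule for confidence limits.

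Intervals for mean changes (endometrial thickness, QTcF, VMS frequency) are optional. If the sponsor considers intervals not applicable to some or all outcomes, SAP Section 10 should say so and give the reason. The denominator correction is needed in either case.

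The cost is SAP wording and an extra column in a few tables. No new data are needed.

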10.3.2 Data handling

Procedures for the handling of any missing, unused, or spurious data will be described in the SAP. Data issues found after database lock will be described in the Clinical Study Report (CSR).

10.3.3 Analysis of demography and other baseline subject characteristics

Demographic and other baseline variables include age, sex, height, weight, ethnic origin, and medical history.

Age, sex, height, weight, ethnic origin will be summarized. Age will be calculated as the integer difference in years from date of birth to informed consent date. Medical history will be summarized in table or listed by subject.

10.3.4 Safety evaluation

The safety analysis is the long-term safety and tolerability of MT-8554 during the OLE period.

The safety endpoints vital signs, ECG parameters, clinical laboratory assessments, physical examinations, AEs, endometrial and breast safety measures, reproductive hormones, and depression [PHQ-8 and GAD7] will be summarized in tables according to the data type. The graphs will be generated for the endpoints as needed. The data will be presented in data listings as needed.

Any other safety data and concomitant medication will be presented in tables or listings as appropriate.

Further details will be provided in the SAP.

10.3.4.1 Adverse events

AEs are considered as treatment emergent if they occur after the first dose administration of study medication of Study MT-8554-A02 or if a pre-dose event increases in severity following dosing. The frequency and incidence of TEAEs will be summarized by System Organ Class (SOC) and Preferred Term (PT), by treatment group and overall. TEAEs will be summarized by treatment, by relationship to study medication and by maximum severity as well. Serious TEAEs and TEAEs leading to study medication discontinuation will be summarized in tables. All AE will be presented in a data listing.

Physical examination data will be listed by subject. Changes in physical examinations will be described in the text of the CSR.

10.3.5 Analysis of efficacy endpoints

The efficacy endpoints include Frequency of VMS, Severity of VMS, and MENQOL.

Frequency of VMS is the average daily frequency of moderate to severe VMS, defined as the sum of the number of moderate to severe VMS during 1 week divided by number of days with data. Severity of VMS is the average daily severity score of mild to severe

VMS. Baseline VMS severity score is defined as $(2xFmo + 3xFse)/(Fmo + Fse)$, and VMS severity score for a specific week during the open label treatment period is defined as $(1xFmi + 2xFmo + 3xFse)/(Fmi + Fmo + Fse)$, where Fmi, Fmo, and Fse are the daily frequencies of mild, moderate, and severe VMS, respectively, during each applicable study week.

All efficacy endpoints and change from baseline of these will be summarized in tables according to the data type. The graphs will be generated for the endpoints as needed. The data will be presented in data listings as needed.

Further details will be provided in the SAP.

11 STUDY MANAGEMENT AND ETHICAL AND REGULATORY REQUIREMENTS

11.1 Good Clinical Practice

The Investigator will ensure that this study is conducted in compliance with the 2013 (Fortaleza, Brazil) revision of the 1964 Declaration of Helsinki. This study will also be conducted in accordance with Good Clinical Practice (GCP) requirements described in the current revision of ICH Guidelines. This study will also be carried out in accordance with regional and local legal requirements. Before the first subject is enrolled in the study, all ethical and legal requirements will be met.

11.2 Investigator responsibilities

11.2.1 Informed consent

Prior to undergoing any study-specific procedure, all legally competent subjects must consent in writing to participate. An IRB/EC approved ICF will be given to each subject.

The process of obtaining the informed consent will be in compliance with all regulatory regulations, ICH requirements, and local laws.

11.2.2 Ethical and regulatory approval

The study was conducted in accordance with ethical principles that have their origins in the Declaration of Helsinki and that are consistent with GCP as described in:

1. Declaration of Helsinki, concerning medical research in humans (Adopted by the 18th World Medical Association [WMA] General Assembly, Helsinki, Finland, June 1964 and amended by the: 29th WMA General Assembly, Tokyo, Japan, October 1975; 35th WMA General Assembly, Venice, Italy, October 1983; 41st WMA General Assembly, Hong Kong, September 1989; 48th WMA General Assembly, Somerset West, Republic of South Africa, October 1996; 52nd WMA General Assembly, Edinburgh, Scotland, October 2000; 53rd WMA General Assembly, Washington DC, USA, October 2002 (Note of Clarification added); 55th WMA General Assembly, Tokyo, Japan, October 2004 (Note of Clarification added); 59th WMA General Assembly, Seoul, Republic of Korea, October 2008; 64th WMA General Assembly, Fortaleza, Brazil, October 2013).
2. ICH Harmonised Tripartite Guidelines for Good Clinical Practice 1996.
3. Food and Drug Administration Code of Federal Regulations (21 CFR).

The Investigator and Sponsor will sign this protocol to confirm agreement to abide by it.

Before any study-related procedure is performed on a subject, all Independent Ethics Committee (IEC), regulatory and local approvals of this protocol will be obtained. While the study is ongoing and at study completion/discontinuation, the Sponsor or Investigator will submit information to the IEC(s) in accordance with institutional/local regulations, for example:

- Information on SUSARs
- Periodic reports on the progress of the study

- Notification of the EOS or early termination
- Final study summary upon completion or closure

The Sponsor will ensure that any SUSARs from this study and other studies with this study medication are reported promptly to the regulatory authorities.

If it is necessary to amend the protocol during the study, proper notification will be made to the regulatory authorities and IRBs in the form of a protocol modification. Protocol modification requiring IRB approval may be implemented only after a copy of the IRB's approval/favorable opinion letter has been transmitted to the Sponsor and regulatory authority approval has been obtained (if required). Protocol modifications that are intended to eliminate an apparent immediate hazard to subjects may be implemented prior to receiving Sponsor, FDA and/or IRB approval. However, in this case, approval must be obtained as soon as possible after implementation.

Any protocol or other deviations that occur during the study will be documented and reported to the Sponsor. Depending on the nature of the deviation, this may be reported to the FDA and the IRB.

